## **4 SAFETY AND ADVERSE EVENTS**

### **4.1 Measures to reduce risk for adverse events**

Risks related to low blood pressure, or hypotension, are minimal but may increase with dehydration/hypovolemia. To reduce this risk, participants will be counseled on maintaining good hydration and diet, and on the potential effects of orthostatic hypotension.

## 4.2 Adverse Event Definitions

**Adverse Event (AE):** Any untoward medical occurrence in a clinical research participant administered an investigational product, which may or may not have a causal relationship with the investigational product. As such, an AE can be an unfavorable or unintended sign (including an abnormal laboratory finding, for example), symptom or disease temporally associated with the use of an investigational product, whether or not considered related to the product.

If a preexisting condition worsens post-enrollment (frequency increases and/or severity grade increases), it should be reported as an adverse event.

A symptom check-list will be included in the CRF (detailed in the protocol implementation manual) that includes common symptoms or side effects typically related to losartan therapy.

**Appendix D** provides a table of adverse events, with grading criteria, adopted from the DAIDS 2009 Table for Grading the Severity of Adult and Pediatric Adverse Events

**Serious Adverse Event (SAE):** Any adverse event occurring at any dose that results in any of the following outcomes:

- i. Death,
- ii. A life-threatening condition,
- iii. A congenital anomaly/birth defect,
- iv. Inpatient hospitalization or prolongation of existing hospitalization,
- v. Persistent or significant disability/incapacity,
- vi. An important medical event that, based upon appropriate medical judgment, may jeopardize the patient or subject and may require intervention to prevent one of the outcomes listed above.

**Unanticipated Problem (UP)** is any event that is:

- i. Unexpected, AND
- ii. Related to study participation in this study, AND
- iii. Increase the risk of harm to the participant or others (or be an SAE)

## 4.3 Documenting Adverse Events

All new adverse events of grade  $\geq 3$  or deemed related to study drug will be ascertained and recorded on study visit CRFs (through the online REDCAP interface). Criteria for assigning a grade of severity of adverse events are summarized in Appendix D.

**NOTE: adverse events based on laboratory criteria will only be ascertained/recorded if  $\geq$  grade 3, and no adverse events will be ascertained/recorded based on CD4+ T-cell count criteria.**

There are five severity grades that can be assigned to adverse events, which are defined as follows:

- i. Grade 1 = Mild

- ii. Grade 2 = Moderate
- iii. Grade 3 = Severe
- iv. Grade 4 = Potentially life-threatening
- v. Grade 5 = Death

Additional information ascertained for each adverse event includes: a) date of onset, b) relationship to study drug (see section 4.4 below), c) any action taken on study drug, and d) whether the adverse event qualifies as a serious adverse event (including the SAE criteria fulfilled).

Source documentation (in addition to the CRF variables for AEs) will be collected at clinical sites for all serious adverse events, as well as any other problems involving risks to participants that are unanticipated or unexpected and are reasonably believed to be related to research participation.

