#### **4.5 Reporting Adverse Events**

The IRB (or Human Subjects Committee) for the site where the event occurred will receive immediate notification of all serious adverse events (SAE) that are ALSO deemed protocol related, OR for any unanticipated problem (UP; which are by definition protocol related). **NOTE:** *an adverse event (of any grade) that is unexpected, is reasonably believed to be related to study participation, and involves risk to the participant or others should be captured as a UP (per definition above 4.2).*

The site will enter this information into the adverse event log and SAE/UP case report form (via REDCap reporting). The data coordinating center (DCC) will distribute a summary of each SAE/UP event to the remaining clinical sites and participating institutions for submission to their respective IRBs.

The site will also complete FDA Form 3500 (MedWatch; see below), and submit this form to the FDA (via online reporting) and also to the DCC. Within 2 business days of learning of the event, clinical sites must:

- a) Inform local IRB per institutional guidelines and timelines

- b) fill out an SAE/UP case report form, via REDCap online reporting
- c) fill out an MedWatch Form FDA 3500
- d) either submit MedWatch Form FDA 3500 to the FDA or complete voluntary reporting online via FDA MedWatch (see below for link)
- e) email the completed MedWatch Form FDA 3500 to: study PI ([name]; [contact]), DCC ([name]; [[contact]](mailto:[contact]))

The DCC will submit FDA Form 3500 and any other information on the SAE/UP from the REDCap CRF, to a representative for Merck Pharmaceuticals. Reporting of all SAE/UP events will be made to FDA and Merck Pharmaceuticals using FDA Form 3500.

FDA MedWatch reporting forms may be found at:  
<http://www.fda.gov/safety/medwatch/howtoreport/downloadforms/default.htm>

FDA MedWatch voluntary reporting can be performed at:  
<https://www.accessdata.fda.gov/scripts/medwatch/>

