## **5.2 Frequency and Content of Data and Safety Monitoring**

To ensure compliance and data are reported correctly and completely, CRF data will be monitored monthly for completeness and compliance with the study protocol. Queries for clarification or data completion will be posted to a site-specific and password protected section of the LIFE-HIV website.

The PI will be informed of serious adverse events as soon as they occur and will notify the NIA and DSMB within 24 hours of notification. During the study the DSMB will meet at least yearly either in-person or by teleconference call to review study progress, data quality, and participant safety. An initial DSMB meeting will be scheduled as soon as any of the following occurs:

- i. Six months have elapsed since enrollment of the first patient
- ii. 50% of goal enrollment is achieved
- iii. 30 person-years of follow-up is achieved

The data and safety monitoring report will include data on: enrollment (including progress), visit attendance, completeness of data, completeness and quality of specimen collection, baseline characteristics, adherence and discontinuation of medication, and side effects and adverse events.

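### Section 4.3's recording rule omits seriousness, so unrelated grade 1-2 SAEs have no stated CRF entry, and 4.5 and 5.2 differ on which SAEs reach the PI and how soon

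*Combined protocol and SAP*

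**What the plan says.** **Definition (4.2).** An SAE is "Any adverse event occurring at any dose that results in any of the following outcomes". The list includes "Inpatient hospitalization or prolongation of existing hospitalization". Neither severity grade nor relatedness enters the definition.

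**Recording (4.3).** New adverse events of grade 3 or higher "or deemed related to study drug will be ascertained and recorded on study visit CRFs (through the online REDCAP interface"). Whether the event is an SAE is one of the items collected for each event. A note adds that "adverse events based on laboratory criteria will only be ascertained/recorded if" they reach grade 3. Separately, "Source documentation (in addition to the CRF variables for AEs) will be collected at clinical sites for all serious adverse events".

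**Relatedness (4.4).** The investigator must assess the relationship to study medication for events of grade 3 or higher after randomization.

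**Reporting (4.5).** The site's IRB "will receive immediate notification of all serious adverse events (SAE) that are ALSO deemed protocol related", and likewise of any unanticipated problem (UP). The site enters this information in the adverse event log and the SAE/UP form. "Within 2 business days of learning of the event, clinical sites must" complete a list of steps, one of which is to email the MedWatch form to the PI and the data coordinating center (DCC). A later sentence says that all SAEs and UPs go to FDA and the manufacturer, and states no relatedness limit.

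**Monitoring (5.1 and 5.2).** The DSMB receives adverse event reports every 3 months. In addition, "The PI will be informed of serious adverse events as soon as they occur and will notify the NIA and DSMB within 24 hours", and that sentence counts the 24 hours from the notification.

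**The concern.** The recording rule has two ways in, grade and relatedness, and seriousness is not one of them. Because SAE status is asked of events that are recorded, a serious event that fails both tests is never asked the question. The SAE tables would then not follow the protocol's own SAE definition, and for low-grade events they would depend on a site judgement of relatedness.

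That matters because Section 5.1 expects any DSMB recommendation to stop to rest on an unacceptably high adverse event rate. With 110 participants planned in Section 2.7, a few absent events could change how a comparison of the arms looks.

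Sections 4.5 and 5.2 raise a second question: whether the people who must tell the NIA and the DSMB about SAEs are themselves told of all of them, and how soon.

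**Working it through.** The plan gives no SAE rate and no figure to reproduce. The check sets the sections side by side and adds two reporting intervals.

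**Step 1. Apply each rule to each kind of SAE.** Here *unrelated* means related neither to study drug nor to the protocol.

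| SAE (4.2) | CRF entry under 4.3 | Pathway under the opening of 4.5 | PI informed under 5.2 |
|---|---|---|---|
| Grade 3-5, related | Yes | Yes | Yes |
| Grade 3-5, unrelated | Yes | No | Yes |
| Grade 1-2, drug-related, not laboratory-based | Yes, once judged related | Yes | Yes |
| Grade 1-2, unrelated | **None stated** | No | Yes |
| Grade 1-2, laboratory-based | **None stated**, even if related | Only if protocol-related | Yes |

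The fourth row is the main gap. Section 4.3 makes grade 5 death and grade 4 potentially life-threatening, so those SAE criteria are recorded whatever the attribution. What remains is low-grade events that meet another criterion, chiefly hospitalization.

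**Step 2. Relatedness.** Section 4.3 admits a grade 1-2 event only if it is deemed related. Section 4.4 requires that assessment only at grade 3 or higher. Entry for lower grades therefore turns on a judgement that 4.4 does not require.

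**Step 3. From the CRF to the DSMB.** Section 3.4 has all data entered on web-based CRFs. An event with no CRF entry can therefore be missing from summaries drawn from them, including the 3-monthly reports. Source papers held at the site do not change that.

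**Step 4. Route to the PI.** The only site-to-PI step described in 4.3 to 4.5 is the emailed MedWatch form in 4.5. That list follows from an opening limited to protocol-related SAEs and UPs. The UP limb does not bring in unrelated SAEs, because 4.2 requires a UP to be related to participation. Section 5.2 says the PI will be informed of SAEs generally, but not by what step.

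**Step 5. Timing for a related SAE.** Longest interval from site awareness to the DSMB = 2 business days (4.5) + 24 hours from PI notification (5.2). Without public holidays:

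| Site learns on | PI told by | Calendar days | Plus 1 day for the PI |
|---|---|---|---|
| Monday | Wednesday | 2 | 3 |
| Tuesday | Thursday | 2 | 3 |
| Wednesday | Friday | 2 | 3 |
| Thursday | Monday | 4 | 5 |
| Friday | Tuesday | 4 | 5 |

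The permitted interval is about 3 to 5 calendar days. A Monday holiday after a Friday event would make it 5 + 1 = 6. These are upper limits; a site may act sooner.

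**The case against.** Five points can be made for the plan.

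*The 24-hour limit is kept.* A reader might infer that 5.2 promises the DSMB every SAE within 24 hours and that 4.5 breaks the promise. The text does not support that. The 24 hours start when the PI is notified, so the two intervals run one after the other and neither is breached. What stands is the mismatch between prompt notice to the PI in 5.2 and 2 business days in 4.5.

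*The events are not lost.* A reader might also infer that unrelated low-grade SAEs vanish. Section 4.3 keeps source documents for every SAE, and describes them as additional to CRF variables, which suggests that CRF data were expected too. Section 5.2 has the PI told of SAEs without restriction, and one sentence of 4.5 covers all SAEs and UPs for FDA and the manufacturer. This shows a wider intent. It supplies neither a recording rule nor a site-to-PI step, and the 4.5 sentence conflicts with the opening of its own section.

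*The gap is narrow.* All grade 3-5 events are recorded whatever their cause. That stands. How many events fall below grade 3 and are still serious depends partly on the grading table in Appendix D, which was not available for this review.

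*Attribution is blinded.* Section 2.4 blinds treatment assignment, so site judgements should not systematically favour one arm. That stands too: the issue is completeness of the safety data more than bias. Section 5.1 also does not define the adverse event rate or tie it to SAEs.

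*Other documents may help.* The DSMB Charter, the data and safety monitoring plan and the implementation manual are cited but were not available, and may describe the missing route. They would not remove the differences between sections of the protocol itself.

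**Conclusion.** The point holds as a gap in the recording rule and a conflict of scope. Followed literally, 4.3 gives no CRF entry to an unrelated grade 1-2 SAE, and 4.4 leaves lower-grade relatedness without a required assessment. Sections 4.5 and 5.2 differ on which SAEs are passed on, and no route to the PI is described for unrelated ones. For related SAEs, the DSMB may hear about 3 to 5 calendar days after the site does, assuming no public holiday and full use of both intervals. That is a possible delay within the stated limits.

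No count of missed SAEs can be given. Any figure would need an assumed SAE rate and an assumed share that is both low-grade and unrelated, and the documents give neither. The efficacy analyses are not affected. The change is worth making because it is cheap and improves the safety data that the DSMB sees.

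**What to change.** - **4.3:** add a third limb to the recording rule, *or serious, regardless of grade or relatedness*, and state that it also overrides the laboratory note.
- **4.4:** require the relatedness assessment for every SAE and for every event whose recording depends on it.
- **4.5:** require the SAE form and the notice to the PI and DCC for every SAE. Reconcile the relatedness limit at the start of the section with the later sentence covering all SAEs and UPs, and say which scope applies to the IRB, to FDA and to the manufacturer.
- **4.5 and 5.2:** reconcile the site-to-PI timing. One workable form is a short alert to the PI first, with the full form following within the 2 business days.

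The cost is revised protocol and CRF instruction wording and slightly more reporting by sites. No treatment rule or efficacy analysis changes.

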### **3.2 Study Drug Dose Modification**

At baseline, participants will start losartan or matching placebo at 50mg daily. At 2 weeks, side effects and blood chemistries (basic metabolic panel [BMP]) will be assessed. The dose of losartan/placebo will increase to 100mg daily at this week 2 visit (i.e., once lab results return) if all of the following criteria are met:

- a) Systolic blood pressure (BP) ≥90 mmHg

- b) Potassium  $\leq 5.0$  mmol/L
- c) eGFR  $\geq 30$  mL/min/1.73m^2
- d) Lack of a grade  $\geq 3$  side effect since the last evaluation deemed possibly/probably related to the study drug.
- e) Lack of significant side effects deemed related to study drug (e.g., lightheaded upon standing)
- f) Lack of other concerns to increase study drug dosing, as determined by site investigator

If participants are increased to 100mg dose at the week 2 visit and continue to tolerate this dose at the month 1 visit, they will be contacted by phone to verify tolerability 2-4 weeks following the month 1 visit. Participants may be evaluated by clinical labs and/or have side effects assessed at any point during the study, per the discretion of the site investigator. If participants are increased to 100mg daily (or matching placebo) they will maintain this dose for the duration of the 12-month study unless new side effects or adverse events necessitate re-evaluation (see below criteria).

If participants do NOT increase dose to 100mg daily at the week 2 visit (e.g., if symptomatic or if systolic BP is not  $\geq 90$  mmHg), the criteria for dose escalation may be reassessed at the 1-month visit. If participants do not meet criteria for dose increase (from 50mg to 100mg daily) after the 1-month visit, they will be maintained on 50mg dose until the month 3 visit, at which time the dose may be increased to 100mg daily if the five criteria above are met (a-e). At any point when participants have dose increased from 50mg to 100mg, they will be contacted by phone within 2 weeks to assess side effects and have clinical labs drawn to assess toxicity; a full study visit for side effect and adverse event documentation can occur at any point, per the discretion of the site investigator.

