Dose Reduction: Tolerability, side effects, and clinical laboratory monitoring will be assessed at each study visit (via participant report and clinical labs), and at any other time point at the discretion of the clinical site investigator. Adverse events that are assessed as related to study drug will prompt re-evaluation via phone or as an adverse event visit, per clinical discretion of the site investigator. If this event worsens or does not resolve after re-evaluation, then study medication dose should be decreased (i.e., from 100mg to 50mg) or stopped (if taking 50mg daily). If signs and symptoms resolve after 2 weeks, then the participant may resume or increase dose (i.e., back to 100mg if previously reduced to 50mg daily), per the clinical discretion of the site investigator.

Stopping Study Medication: If an adverse event of grade  $\geq 3$  is assessed as related to study drug, study medication should be stopped and the participant should be re-evaluated in 2 weeks. If a grade 2 rash is persistent, study medication may also be stopped at the discretion of the site investigator and the participant should be re-evaluated in 2 weeks. If signs and symptoms resolve after 2 weeks, then the participant may be re-challenged at a lower dose (i.e., at 50mg if previously taking 100mg daily) per the clinical discretion of the site investigator. If study medication is stopped for an adverse event that is later determined NOT to be related to study medication, then the

medication may be resumed at 50mg and increased to 100mg per initial criteria for dose escalation and at the discretion of the clinical site investigator.

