#### **4.4 Adverse Event Relationship to Study Drug**

For all adverse events grade  $\geq 3$  that occur after randomization, study investigator(s) will assess the potential relationship of the event to the study medication. One of the following designations will be used:

- i. Related: There is a reasonable possibility that the AE may be related to the study agent(s).
- ii. Not related: There is not a reasonable possibility that the AE may be related to the study agent(s). Alternative etiology, diagnosis or, explanation for the AE should be provided.

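### The grade 3 floor for laboratory adverse events in section 4.3 leaves out of the AE record a related lower-grade laboratory event that changes the dose under section 3.2

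*Combined protocol and SAP*

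**What the plan says.** Section 4.3 opens with a general rule: new AEs of grade 3 or higher "or deemed related to study drug will be ascertained and recorded on study visit CRFs". Under that sentence a related event is recorded at any grade. The bold NOTE that follows narrows it for one class of event: "adverse events based on laboratory criteria will only be ascertained/recorded if" they are grade 3 or higher. The NOTE also exempts CD4+ count from AE recording. It contains no exception for laboratory events that are related or that change dosing. Each recorded AE carries further fields, among them "relationship to study drug (see section 4.4 below), c) any action taken on study drug". Section 4.4 says that, for AEs of grade 3 or higher after randomization, "study investigator(s) will assess the potential relationship of the event to the study medication".

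Section 3.2 sets the dosing rules. A participant on 100mg stays there: "they will maintain this dose for the duration of the 12-month study unless new side effects or adverse events necessitate re-evaluation". Under Dose Reduction, a related AE prompts re-evaluation, and then: "If this event worsens or does not resolve after re-evaluation, then study medication dose should be decreased (i.e., from 100mg to 50mg) or stopped", the stop applying to those on 50mg. No grade is named. Under Stopping Study Medication, for a related AE of grade 3 or higher, "study medication should be stopped and the participant should be re-evaluated in 2 weeks". Laboratory checks feed these rules. After any step from 50mg to 100mg, for instance, "they will be contacted by phone within 2 weeks to assess side effects and have clinical labs drawn to assess toxicity".

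**The concern.** The dosing rule and the recording rule use different thresholds. Section 3.2 acts on relatedness and persistence, whatever the grade. For laboratory events, section 4.3 records on grade alone. An investigator can follow both sections exactly, lower a participant's dose for a laboratory toxicity judged to be drug-related, and make no AE entry.

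Potassium and eGFR are the two laboratory measures on which section 3.2 conditions the step to 100mg, so they are natural candidates for such events. Tolerability is a named secondary outcome in section 2.5, and section 3.3 pairs it with laboratory toxicity assessment. Section 5.1 says that a DSMB recommendation to stop would probably rest on the AE rate. If tolerability is summarised from AE records, dose-changing laboratory toxicity below grade 3 is missing from both.

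**Working it through.** There is no stated figure to reproduce. The check is a comparison of the rules.

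1. **Is an abnormal laboratory result an AE?** Yes. The definition in section 4.2 includes it. The NOTE in 4.3 limits what is ascertained and recorded and does not rewrite that definition.

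2. **Can a grade 1 or 2 laboratory AE change the dose?** Yes. The Dose Reduction paragraph opens by listing laboratory monitoring among the assessments at each visit. It then acts on related AEs that worsen or fail to resolve, with no grade floor and no exclusion of laboratory events. Related events of grade 3 or higher have their own stop rule, so the reduction rule works mainly below grade 3.

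3. **Is that event recorded?** Applying section 4.3 case by case:
   - Related symptom, grade 1 or 2: recorded, under the general rule.
   - Laboratory AE, grade 3 or higher: recorded, under both the general rule and the NOTE.
   - Unrelated AE of any type, grade 1 or 2: not recorded, already under the general rule.
   - Related laboratory AE, grade 1 or 2, no dose change: not recorded, because of the NOTE.
   - Related laboratory AE, grade 1 or 2, dose reduced or stopped: not recorded, because of the NOTE. The AE fields for relatedness and for action on study drug are then not completed.

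   The last case is the gap.

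4. **Does another reporting route catch it?** Only in part. Section 4.5 covers related SAEs and unanticipated problems. An unanticipated problem may be of any grade but must be unexpected. Potassium and renal changes are largely anticipated here: potassium above 5.0 mmol/L is an exclusion in section 2.3, kidney damage is a listed risk in section 2.4, and both measures are escalation criteria in section 3.2.

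5. **What survives elsewhere?** Table 2 schedules a basic metabolic panel (BMP) at every visit, so raw values can be compared by arm. Section 5.2 lists discontinuation of medication as DSMB report content, separately from AEs. It names neither dose reduction nor laboratory values. Section 6 specifies no analysis of laboratory safety or dose changes. The unprotected case is therefore chiefly a reduction from 100mg to 50mg.

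6. **How many participants?** The documents give no rate. For scale only, take the 110 participants of section 2.7, so 110 / 2 = 55 on losartan. If 1% to 10% had such an event, 55 × 0.01 = 0.55 to 55 × 0.10 = 5.5 participants would be affected. That range is an assumption with no anchor in the documents.

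**The case against.** The best case for the plan is that the NOTE is deliberate. It is bolded, sits directly after the general rule and stands beside a parallel CD4+ exemption. A floor on laboratory AEs saves work, and no one goes unmonitored: panels are drawn at every visit and investigators may check laboratory values at any time. This stands as a defence of a floor in general. It does not explain why an event serious enough to change the dose should be treated like an incidental abnormality.

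One could also argue that a laboratory finding below grade 3 is not an AE for this trial, so section 3.2 is never triggered. The definition in 4.2 says otherwise. If that reading were right, such dose changes would rest on site discretion and would still be unrecorded as AEs.

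A reader might infer more than the documents support, in four ways:

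- That the relatedness judgement is never made. Section 4.4 requires it from grade 3 but does not forbid it below, and a dose cut under 3.2 presupposes it. Only its entry in the AE record is lost, and another case report form may hold the reason for a dose change.
- That the DSMB cannot see these participants. Those who discontinue are reported under section 5.2.
- That two of the five severity grades are lost because of the NOTE. Unrelated grade 1 and 2 events of every type are already left out by the general rule; the NOTE removes only the related laboratory ones.
- That participants on 100mg have no laboratory action limits. Section 3.2 gives no potassium or eGFR value for them, but the stop rule works through the grading table in Appendix D. That table, like the DSMB Charter, was not available for this review.

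**Conclusion.** The concern holds in a narrow form and is minor. The two sections, read together, leave out of the AE record any related grade 1 or 2 laboratory AE that changes dosing, unless it is an SAE or an unanticipated problem. The main loss is the documented link from event to dose action, chiefly for reductions from 100mg to 50mg, and with it some completeness of the AE rate and of any tolerability summary built on AE records.

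This conclusion does not depend on the cut-offs in Appendix D, since a floor at grade 3 presupposes lower laboratory grades. It does assume that no other form captures the same link, which cannot be checked. The frequency is unknown. The intention-to-treat analysis of log IL-6 is not affected.

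**What to change.** Amend the NOTE in section 4.3 so that a laboratory AE is recorded if it is grade 3 or higher, or at any grade if it is assessed as related under section 3.2 and leads to study drug being reduced, withheld or stopped. Keep the CD4+ exemption. Extend section 4.4 to the same events. The cost is a protocol wording change and a few extra AE entries. No extra blood draws are needed.

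Recording every related low-grade laboratory AE is not recommended. It would ask investigators to judge relatedness for each minor abnormality across up to 6 post-baseline BMPs × 110 = 660 panels, plus 4 CBC and hepatic assessments × 110 = 440, for little gain.

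Two additions are optional. On-treatment action values for potassium and eGFR could be stated in section 3.2 if Appendix D does not already supply them. Potassium and eGFR by arm could be added to the closed DSMB report if the Charter or the monitoring plan does not already require them.
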